	16.2.6.1	Investigator's Global Assessment (IGA)	ITT Population
	16.2.6.2	Eczema Area and Severity Index (EASI)	ITT Population
	16.2.6.3	Weekly Average Pruritus and Sleep Disturbance Numeric Rating Scale	ITT Population
	16.2.6.4	Daily Pruritus and Sleep Disturbance Numeric Rating Scale	ITT Population
	16.2.6.5	Weekly Average Sleep Metrics	ITT Population
	16.2.6.6	Subject Sleep Diary	ITT Population
	16.2.6.7	Body Surface Area Involvement of AD	ITT Population
	16.2.6.8	SCORing Atopic Dermatitis (SCORAD)	ITT Population
	16.2.6.9	Pain Frequency and Intensity	ITT Population
	16.2.6.10	Days of Application of Topical Medication for Atopic Dermatitis	ITT Population

This document is confidential.

1.0

CD14152:SPR118161:SAP.V01

Approved 10-Nov-2022 00:00:00

Header	Listing Number	Name	Analysis Set
	16.2.6.11	Daily Topical AD Medication Use	ITT Population
	16.2.6.12	Patient Global Assessment of Disease (PGAD) and Treatment (PGAT)	ITT Population
	16.2.6.13	Weekly Average Pruritus Categorical Scale (PCS)	ITT Population
	16.2.6.14	Daily Pruritus Categorical Scale (PCS)	ITT Population
	16.2.6.15	Patient Global Impression of Severity (PGIS) and Change (PGIC) for Pruritus and Sleep Disturbance – PGIS-P, PGIS-SD, PGIC-P, PGIC-SD	ITT Population
	16.2.6.16	Dermatology Life Quality Index (DLQI)	ITT Population
	16.2.6.17	Children’s Dermatology Life Quality Index (cDLQI)	ITT Population
	16.2.6.18	Patient-Oriented Eczema Measure (POEM)	ITT Population
	16.2.6.19	Hospital and Anxiety Depression Scale (HADS)	ITT Population
	16.2.6.20	Work Productivity and Activity Impairment: Atopic Dermatitis (WPAI:AD)	ITT Population
	16.2.6.21	EuroQoL 5-Dimension (EQ-5D)	ITT Population
16.2.7		Adverse Event Listings	
	16.2.7.1	Treatment Emergent Adverse Events (TEAE)	Safety Population
	16.2.7.2	Pre-Treatment Adverse Events	Safety Population
	16.2.7.3	Treatment Emergent Adverse Events (TEAE)	Safety Population – Subjects with COVID-19 Infection
	16.2.7.4	Treatment Emergent Adverse Events (TEAE) comments	Safety Population
	16.2.7.5	Adjudicated Asthma Treatment Emergent Adverse Events (TEAE)	Safety Population
	16.2.7.6	Adjudicated Asthma Treatment Emergent Adverse Events (TEAE) Comments by Independent Adjudication Committee	Safety Population
16.2.8		Listing of Individual Laboratory Measurements by Subject	
16.2.8.1		Clinical Laboratory Data	
	16.2.8.1.1	Laboratory Data - Hematology	Safety Population
	16.2.8.1.2	Laboratory Data – Clinical Chemistry	Safety Population
	16.2.8.1.3	Laboratory Data - Urinalysis	Safety Population
	16.2.8.1.4	Childbearing Potential and Premenses Status	Safety Population
	16.2.8.1.5	Pregnancy Test Results	Safety Population
	16.2.8.1.6	Tuberculosis Test Results	Safety Population
	16.2.8.1.7	Virology	Safety Population
16.2.8.2		Other Safety Data	
	16.2.8.2.1	Vital Signs, Height and Weight	Safety Population
	16.2.8.2.2	Electrocardiogram (ECG)	Safety Population
	16.2.8.2.3	Physical Examination	Safety Population
	16.2.8.2.4	Respiratory Assessment – Medical Interview	Safety Population

This document is confidential.

Statistical Analysis Plan for Interventional Studies

Sponsor: Galderma Research & Development, LLC; Protocol No.: RD.06.SPR.118161

Header	Listing Number	Name	Analysis Set
	16.2.8.2.5	Respiratory Assessment – Peak Expiratory Flow (PEF)	Safety Population
	16.2.8.2.6	Known Asthma, Wheeze, Dyspnea and Cough Triggers	Safety Population
	16.2.8.2.7	Asthma Control Test (ACT)	Safety Population
	16.2.8.2.8	Subjects with a drop by $\geq 15\%$ from Baseline for either PEF or ACT	Safety Population
	16.2.8.2.9	Immunogenicity - Anti-drug Antibody (ADA) and Neutralizing Antibodies	PK Population

1.0

CD14152.SPR118161.SAP.V01

Approved 10-Nov-2022 00:00:00

This document is confidential.

22. Appendices

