Based on the phase 2b results (Protocol 114322), it is estimated that 15% of subjects will drop out from the initial treatment period. Assuming a 45% responder rate in active treatment and 12% with placebo, approximately 216 subjects will participate in the maintenance period (190 nemolizumab and 26 placebo subjects).

Table 2: Maintenance Period Re-Randomized Group Assignments

Group	Treatment	Dose	Week(s)	Route	Schedule
1A	Nemolizumab (CD14152)	30 mg	16, 20, 24, 28, 32, 36, 40, 44	sc	Q4W
1B	Nemolizumab (CD14152)	30 mg	16, 20*, 24, 28*, 32, 36*, 40, 44*	sc	Q8W*
1C	Placebo	Placebo	16, 20, 24, 28, 32, 36, 40, 44	sc	Q4W

**with placebo Q4W at Week 20, 28, 36, and 44 to maintain blind*

Abbreviation(s): Q4W=every 4 weeks; Q8W=every 8 weeks; sc=subcutaneous.

Beginning at Week 16, subjects in group 1A will receive active (ie, nemolizumab [CD14152]) study drug injections Q4W up to Week 44. Subjects in group 1B will receive active study drug injections Q8W, with placebo at alternating visits to maintain the blind. Group 1B subjects will receive the last active study drug injection at Week 40 (final injection at Week 44 will be placebo). Group 1C subjects will receive placebo Q4W (ie, through Week 44).

Subjects should continue the same background topical therapy used in the initial treatment period leading up to the Week 16 visit, including tapering or complete cessation (no use), if applicable. Throughout the maintenance period, adjustments to background topical therapy, as determined by the investigator, are permitted based on the subject's clinical response.

Primary maintenance effect will be evaluated based on Week 48 assessments. All maintenance endpoints will be analyzed independently from each pivotal study and by using pooled data after the completion of both trials.

CONFIDENTIAL

Subjects requiring rescue therapy before the Week 32 visit must undergo a required wait period (with continued study visits) until the Week 32 visit, at which time they may be considered for LTE eligibility/participation. Thereafter, no wait period is required.

Subjects who complete the Week 48 visit may be eligible to enroll into the LTE study (Protocol 118163). Subjects requiring rescue medication before the Week 48 visit may be considered for LTE eligibility. The follow-up visit is not required for subjects who participate in the LTE study.

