8.4.9.1.3 Rescue Therapy

If deemed to be medically necessary by the investigator (eg, to control intolerable AD signs/symptoms), rescue therapies can be prescribed to the subjects at any time during the study, except during the run-in period. (Subjects receiving rescue therapies during the run-in period are not eligible to participate in the study.)

As a general guideline and per individual investigator judgment, rescue therapy should not be prescribed within the first 2 weeks after baseline (ie, Week 2) to allow a minimum time for study drug exposure in the presence of background therapy.

Rescue treatments are only treatments that directly treat AD (mainly those that are approved or are standard of care) and include topical and systemic treatments as outlined. Rescue therapies include:

- Higher potency of TCS (equivalent to class I-II according to the US classification)²
- Oral corticosteroids
- Biologics (including their biosimilars)
- Systemic nonsteroidal immunosuppressants/immunomodulators
- Phototherapy

Antihistamines, sleep aids, topical and systemic antibiotics, and anti-itch creams are **not** considered to be rescue therapy because they do not directly treat AD.

Whenever possible, investigators should first use topical medication as rescue therapy before escalating to systemic therapies. If subjects receive topical treatments or phototherapy as rescue therapy, study drug administration should be continued unless there is a safety concern according to the investigator's judgment. If subjects receive systemic rescue therapy, the study drug administration must be permanently discontinued.

CONFIDENTIAL

For the purpose of efficacy analysis, subjects receiving any rescue therapies will be considered as treatment failures (ie, non-responders). Investigator assessments of efficacy should be performed before initiating rescue therapy. Subjects requiring rescue therapy between scheduled visits should return to the clinic (unscheduled visit) for investigator assessment of efficacy before starting rescue therapy. Further, the use of any rescue therapies should be documented in the CRF.

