8.5.1 Early Termination Visit

Subjects may discontinue from the study or discontinue the study treatment only and continue to participate in the study.

Subjects who prematurely discontinue from the study should undergo final study assessments according to the following guidelines:

- Subjects discontinued from the study during the initial treatment period on/before the Week 16 visit should attend an ET visit. A follow-up/final visit is required 12 weeks after the last study drug administration.
- Subjects discontinued from the study during the maintenance period should attend an ET visit.

A follow-up/final visit is required 12 weeks after the last study drug administration.

Subjects who prematurely discontinue the study drug will be asked to continue participation in the study and return for all remaining visits and assessments (including daily assessment of pruritus, sleep disturbance, etc). Participation will continue until the subject completes the final study visit or otherwise discontinues study participation.

Subjects requiring rescue medication (with or without study medication discontinuation) may be eligible for LTE study participation:

- Subjects requiring rescue medication during the initial treatment period should continue with study visits including the Visit 6/Week 16. A follow-up/final visit is not required for subjects participating in the LTE study.
- During the maintenance period, for subjects requiring rescue medication before the Week 32 visit, a wait period with continuing study visits until the Week 32 visit is due is required. Thereafter, no wait period is required. Subjects must complete the final study/ET assessments prior to rollover to the LTE study.

A follow-up visit is not required for subjects who will participate in the LTE.

CONFIDENTIAL

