8.3. Missing Data

The data after the receipt of rescue therapy will be handled before imputation as below:

Use of rescue therapy: Except OC, all efficacy data on or after the receipt of rescue therapy will be considered as 'not evaluable data' for analysis. For analysis purpose it will be replaced by the worst possible score for endpoint and considered as 'treatment failure'. However, in OC analysis, all observed data even after the receipt of rescue treatment will be included for analysis, i.e., no imputation for missing data.

In case of diary data, if the date of rescue therapy use is within the analysis visit window, the subject at the analysis visit will be treated as treatment failure except for OC analysis, and the weekly average will be imputed using the worst-case value.

Further details for the data handling for rescue therapy are in section 7.

The primary method to impute the missing values will be as follows:

Continuous Endpoints: For continuous endpoints during Initial Period, the MI under MAR assumption approach and the MMRM approach will be used to handle the missing data for the selected secondary endpoints.

QoL endpoints (e.g., DLQI/cDLQI, EQ-5D, PIQ) may be imputed using last observation carried forward (LOCF), where applicable.

Binary Endpoints: All missing values will be treated as a non-responder for the binary endpoints for primary, key secondary and secondary endpoints during Initial Period. To assess the robustness of non-responder analysis for primary and key secondary endpoints, a tipping point analysis will be performed. The MI under MAR assumption, LOCF, and OC will be used as sensitivity analysis to impute the missing values for the primary and key secondary endpoints.

Adverse events and concomitant medications/procedures: Missing assessment times will have imputed times for the purposes of assessing treatment emergence for AEs or classifying medications/procedures into prior/concomitant. However, the assessment times (start date, stop date, and time if collected from CRF) without imputation will be presented in the listings.

For the start of a concomitant medication/procedure or AE:

- Only the year is reported: If the subject received the first study drug dose in the year reported, then the date of the first dose of study drug will be used as the start date; otherwise, January 1 of the year reported will be used as the start date.

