8.4. Analysis Visit Windows

Efficacy by-visit summaries will use the analysis visit. Unscheduled and early termination visits will be windowed based on the following analysis visit window which is based on study day. If multiple measurements are taken within the same window, the one taken closest to the target study day will be used for the analysis. If there are multiple measurements with same difference from target day, the later assessment should be used for the analysis.

Table 8-1: Analysis Visit Window

Analysis Visit	Target Study Day	Visit Window for EASI, IGA, BSA, SCORAD, Rescue therapy	Visit Window for PGIS-P, PGIS-SD, PGIC-P, PGIC-SD	Visit Window for DLQI/cDLQI, HADS, EQ-5D, POEM, WPAI:AD, Pain intensity/frequency, PGAD, PGAT, PIQs*
Baseline	1	<=1	<=1	<=1
Week 4	29	2 to 42	NA	NA
Week 8	57	43 to 70	2 to 81	2 to 84
Week 12	85	71 to 98	NA	NA
Week 15	106	NA	82 to 108	NA
Week 16	113	99 to 126	>=109	85 to 168 except for PIQs; >=85 for PIQs
Week 20	141	127 to 154	NA	NA
Week 24	169	155 to 182	NA	NA
Week 28	197	183 to 210	NA	NA
Week 32	225	211 to 238	NA	169 to 280 except for PIQs
Week 36	253	239 to 266	NA	NA
Week 40	281	267 to 294	NA	NA
Week 44	309	295 to 322	NA	NA

This document is confidential.

Statistical Analysis Plan for Interventional Studies

Sponsor: Galderma Research & Development, LLC; Protocol No.: RD.06.SPR.118161

Week 48	337	>=323	NA	>=281 except for PIQs
---------	-----	-------	----	-----------------------

* PIQs assessment is available during Initial period only. Visit window after Week 16 will not be applicable for PIQs.

Analysis visit of diary (ePRO) data will be defined depending on the data collection as below.

For the diary data at post-baseline visit, only the diary data assessed within the timeframe below (+1 hour to end time in spec) will be considered for analysis. If >1 diary recorded on a day (within window), only one of them to take for analysis (i.e. latest one for evening diary, earliest one for morning diary).

- Evening assessment (PP/AP NRS, Topical medication, PCS) recorded from 17:00:00 to 00:59:59
- Morning assessment (SD NRS, morning sleep diary) recorded from 5:00:00 to 17:59:59

Consecutive daily assessment:

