"Itch-free days" will be defined if PP/AP NRS score is 0 or 1. The proportion of "itch-free days" will be calculated using 7 days diary data for the visit. A minimum of 4 daily scores out of the 7 days for the visit is required for the proportion calculation. The proportion of "itch-free days" will be calculated using number of days of PP/AP NRS score of 0 or 1 divided by number of days reported during the week. The summary of proportion of "itch-free days" based on PP NRS/AP NRS will be presented for Initial Period.

[figure not shown]
During Maintenance Period:

PP/AP NRS will be determined by an average using 7 days data before the visit for Week 24, Week 32, Week 40, Week, Week 48 as a continuous variable for the Maintenance Period. Absolute change and percent change from Baseline and Maintenance Baseline (Week 16) for the PP/AP NRS score will also be included in the summary. No hypothesis testing will be performed.

Improvement in PP/AP NRS will be calculated using Baseline and Maintenance Baseline (Week 16) as the reference point for change in PP/AP NRS score. The proportion of subjects with an improvement of PP/AP NRS ≥ 4 and the proportion of subjects with a PP/AP NRS < 2 will be summarized.

[figure not shown]
For the subset of patients achieving an improvement of PP/AP NRS ≥ 4 at Week 16, the proportion of subjects achieved such an improvement at each analysis visit during the Maintenance Period will be summarized. For the subset of patients achieving a PP/AP NRS < 2 at Week 16, the proportion of subjects with PP/AP NRS < 2 at each visit during the Maintenance Period will be summarized using OC.

Line plot for proportion of subjects with PP NRS improvement ≥ 4 and for proportion of subjects with PP NRS < 2 using Non-responder imputation will be presented for Maintenance Period on the ITT population.

This document is confidential.

CCI

[figure not shown]
1.0

CD14152.SPR118161.SAP.V01

Approved 10-Nov-2022 00:00:00

This document is confidential.

CCI

[figure not shown]
1.0

CD14152.SPR118161.SAP.V01

Approved 10-Nov-2022 00:00:00

This document is confidential.

CCI

1.0

CD14152.SPR118161.SAP.V01

[figure not shown]
Approved 10-Nov-2022 00:00:00

This document is confidential.

[figure not shown]
1.0

CD14152.SPR118161.SAP.V01

Approved 10-Nov-2022 00:00:00

CCI

[figure not shown]
1.0

CD14152.SPR118161.SAP.V01

Approved 10-Nov-2022 00:00:00

This document is confidential.

CCI

[figure not shown]
1.0

CD14152.SPR118161.SAP.V01

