	14.2.2.5.10	Analysis of Proportion of Subjects with an IGA Success and Weekly Average PP NRS Improvement ≥ 4 at Week 16 - Missing as Non-Responder – Initial Period	ITT Population – Excluding Subjects using different version of IGA
	14.2.2.5.11	Analysis of Proportion of Subjects with an IGA Success and Weekly Average PP NRS Improvement ≥ 4 by Visit - Missing as Non-Responder – Initial Period	ITT Population – Excluding Visits under Pandemic
14.2.2.6		Primary and Key Secondary Endpoints	
	14.2.2.6.1	Forest Plot for Primary and Key Secondary Endpoints – Missing as Non-Responder – Initial Period	ITT Population
14.2.3		Secondary Efficacy Parameters	
14.2.3.1		Secondary Efficacy Parameter: IGA	
14.2.3.1.1		Secondary Efficacy Parameter: IGA – Initial Period	
	14.2.3.1.1.1	Summary of IGA – OC - Initial Period	ITT Population
	14.2.3.1.1.2	Summary of IGA - OC - Initial Period	PP Population
	14.2.3.1.1.3	Summary of Proportion of Subjects with IGA Success - Initial Period	ITT Population
	14.2.3.1.1.4	Analysis of Proportion of Subjects with an IGA Success - Missing as Non-Responder – Initial Period	ITT Population
	14.2.3.1.1.6	Analysis of Proportion of Subjects with IGA Success and Weekly Average PP NRS Improvement ≥ 4 - Missing as Non-Responder – Initial Period	ITT Population
	14.2.3.1.1.7	Sensitivity Analysis of Proportion of Subjects with IGA Success and Weekly Average PP NRS Improvement ≥ 4 - Missing as Non-Responder , Using at Least 3 Assessments– Initial Period	ITT Population

This document is confidential.

Header	Table Number	Name	Analysis Set
	14.2.3.1.1.8	Sensitivity Analysis of Proportion of Subjects with IGA Success and Weekly Average PP NRS Improvement ≥ 4 - Missing as Non-Responder , Using at Least 2 Assessments– Initial Period	ITT Population
14.2.3.1.2		Secondary Efficacy Parameter: IGA – Maintenance Period	
	14.2.3.1.2.1	Summary of IGA – OC – Maintenance Period	Enrolled Subjects in Maintenance Period Population
	14.2.3.1.2.2	Summary of Proportion of Subjects with IGA Success - Maintenance Period	Enrolled Subjects in Maintenance Period Population
	14.2.3.1.2.4	Summary of Proportion of Subjects Maintaining IGA Success - OC - Maintenance Period	Enrolled Subjects in Maintenance Period Population – Subjects with IGA success at Week 16
	14.2.3.1.2.5	Summary of Proportion of Subjects with IGA Success and Weekly Average PP NRS Improvement ≥ 4 – OC - Maintenance Period	Enrolled Subjects in Maintenance Period Population

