	14.2.3.2.2.3	Summary of Proportion of Subjects with EASI-50, EASI-75 and EASI-90 - Maintenance Period	Enrolled Subjects in Maintenance Period Population
	14.2.3.2.2.5	Summary of Proportion of Subjects Maintaining EASI-75 – OC - Maintenance Period	Enrolled Subjects in Maintenance Period Population – Subjects with EASI-75 at Week 16
	14.2.3.2.2.6	Summary of Proportion of Subjects with EASI-75 and Weekly Average PP NRS Improvement ≥ 4 – OC - Maintenance Period	Enrolled Subjects in Maintenance Period Population
	14.2.3.2.2.7	Summary of Proportion of Subjects with EASI-75 and Weekly Average PP NRS Improvement ≥ 4 – OC - Maintenance Period	Enrolled Subjects in Maintenance Period Population – Subjects with EASI-75 and PP NRS Improvement ≥ 4 at Week 16
14.2.3.3		Secondary Efficacy Parameter: PP NRS	
14.2.3.3.1		Secondary Efficacy Parameter: PP NRS – Initial Period	
	14.2.3.3.1.1	Summary of Weekly Average PP NRS – OC - Initial Period	ITT Population

This document is confidential.

Header	Table Number	Name	Analysis Set
	14.2.3.3.1.2	Summary of Weekly Average PP NRS – OC - Initial Period	PP Population
	14.2.3.3.1.3	Summary of Proportion of Subjects with Weekly Average PP NRS Improvement ≥ 4 - Initial Period	ITT Population
	14.2.3.3.1.4	Analysis of Proportion of Subjects with Weekly Average PP NRS Improvement ≥ 4 - Missing as Non-Responder – Initial Period	ITT Population
	14.2.3.3.1.6	Analysis of Proportion of Subjects with Weekly Average PP NRS < 2 - Missing as Non-Responder – Initial Period	ITT Population
	14.2.3.3.1.8	Analysis of Change from Baseline in Weekly Average PP NRS – ANCOVA using MI-MAR - Initial Period	ITT Population
	14.2.3.3.1.9	Analysis of Change from Baseline for Weekly Average PP NRS – MMRM Analysis - Initial Period	ITT Population
	14.2.3.3.1.10	Summary of Proportion of Itch-free Days based on PP NRS - OC - Initial Period	ITT Population
	14.2.3.3.1.11	Analysis of Percent Change from Baseline for Weekly Average PP NRS – MMRM Analysis - Initial Period	ITT Population
	14.2.3.3.1.12	Sensitivity Analysis of Proportion of Subjects with Weekly Average PP NRS Improvement ≥ 4 - Missing as Non-Responder, Using at Least 3 Assessments – Initial Period	ITT Population
	14.2.3.3.1.13	Sensitivity Analysis of Proportion of Subjects with Weekly Average PP NRS Improvement ≥ 4 - Missing as Non-Responder, Using at Least 2 Assessments – Initial Period	ITT Population

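### Maintained IGA success and EASI-75 are tabulated as observed case only, so a rescued subject can count as maintaining response or leave the Week 48 denominator

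*SAP*

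**What the plan says.** SAP section 19 (Index of Tables) lists table 14.2.3.1.2.4 as "Summary of Proportion of Subjects Maintaining IGA Success - OC - Maintenance Period" and table 14.2.3.2.2.5 as "Summary of Proportion of Subjects Maintaining EASI-75 – OC - Maintenance Period". Each is restricted to maintenance subjects who met that endpoint at Week 16. Nine maintenance tables use a Week 16 responder subset. Eight carry the OC label; the ninth, 14.2.3.3.2.4 (PP NRS improvement of at least 4), names no method. No non-responder version in these subsets is listed. For subjects with PP/AP NRS below 2 at Week 16, the SAP 10.3.3 text agrees: the proportion still below 2 "at each visit during the Maintenance Period will be summarized using OC".

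SAP 8.3 defines the method: "in OC analysis, all observed data even after the receipt of rescue treatment will be included for analysis", with no imputation. The same section states the missing-as-non-responder rule for the Initial Period.

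Protocol 8.4.9.1.3 says, for efficacy analysis and without limiting it to one period: "subjects receiving any rescue therapies will be considered as treatment failures (ie, non-responders"). It also has study drug normally continuing after topical or phototherapy rescue, so a rescued subject can stay under assessment.

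A rescued subject can also leave early. The protocol synopsis says: "Subjects requiring rescue medication before the Week 48 visit may be considered for LTE eligibility". Section 8.5.1 imposes a wait if rescue comes before Week 32, and then: "Thereafter, no wait period is required". Exit data do not move forward to Week 48, because SAP 8.4 says: "Unscheduled and early termination visits will be windowed based on the following analysis visit window which is based on study day". For IGA and EASI the Week 48 window opens at Day 323.

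**The concern.** Evaluating maintenance treatment is the trial's secondary objective. Protocol 8.2.1 describes the period as a comparison of two dosing regimens with placebo, and protocol 8.1 names Week 48 as the time point for the main maintenance effect. The subjects in that comparison have been re-randomised.

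Rescue and roll-over both happen after re-randomisation. An OC table gives a rescued subject one of three outcomes: maintained (if the criterion is met after rescue), not maintained (if seen and the criterion is not met), or absent (if the subject has left). Only the second agrees with the protocol's rescue-as-failure rule. The visible part of the protocol's relapse definition is worsening that requires rescue, so one subject could be a relapse in table 14.2.3.23.1 and a maintained response in 14.2.3.1.2.4. A reader with only the OC percentages could not tell how much of a difference between arms reflects control of disease and how much reflects who was rescued and who left.

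**Working it through.** **The plan's own figure.** The only stated number for this period is its size: 216 subjects (190 nemolizumab, 26 placebo). From 750 randomised 2:1, 15% dropout and responder rates of 45% and 12%: 500 × 0.85 × 0.45 = 191.25; 250 × 0.85 × 0.12 = 25.5; total 216.75. This reproduces, and gives about 190/3 ≈ 63 per re-randomised arm.

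**The exit gap.** Week 32 is Day 225 and the Week 48 window starts at Day 323. Roll-over on Days 225 to 322 (98 days, 14 weeks) leaves no Week 48 value.

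**Formulas.** For one arm, let r be the fraction rescued, p the response if unrescued, L the fraction of rescued subjects who leave before the Week 48 window, and q the response among rescued subjects who stay.

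- Rescue as failure: (1 − r)p
- OC: [(1 − r)p + r(1 − L)q] / [1 − rL]

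The OC numerator is never smaller than (1 − r)p and its denominator is never larger than 1. So within an arm OC is always equal to or above rescue as failure. The two are equal only if there is no rescue, or if all rescued subjects stay and none responds (leaving aside p = 0).

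**Worked example (all rates assumed).** r = 0.10 on Q4W and 0.40 on placebo; p = 0.85 in both; L = q = 0.5.

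- Rescue as failure: 0.90 × 0.85 = 76.5%; 0.60 × 0.85 = 51.0%; difference 25.5 points.
- OC, Q4W: (0.765 + 0.10 × 0.5 × 0.5) / (1 − 0.05) = 0.790/0.95 = 83.2%.
- OC, placebo: (0.510 + 0.40 × 0.5 × 0.5) / (1 − 0.20) = 0.610/0.80 = 76.3%.
- OC difference: 6.9 points.

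**Range**, with L (0 to 1) and q (0 to 0.85) the same in both arms:

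| Rescue, Q4W / placebo | Response if unrescued | Difference, rescue as failure | Difference, OC |
|---|---|---|---|
| 10% / 40% | 85% / 85% | 25.5 | 0 to 25.5 |
| 10% / 40% | 85% / 70% | 34.5 | 9.0 to 34.5 |
| 10% / 20% | 85% / 85% | 8.5 | 0 to 8.5 |
| 10% / 20% | 85% / 70% | 20.5 | 12.0 to 20.5 |

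With more rescue on placebo, OC shrinks the difference or leaves it unchanged in every row.

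**It can also grow.** With rescue 20% in both arms and response if unrescued 80% on active and 50% on placebo, rescue as failure gives 64% − 40% = 24 points. If all rescued subjects leave, OC gives 80% − 50% = 30 points.

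**The case against.** Much of the case on the other side stands.

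- **No rule is broken.** The protocol synopsis makes maintenance descriptive and places non-responder imputation under the Initial Period, and protocol 10.1.10 exempts OC from its rescue rule. A reader might infer an undeclared departure from protocol; the documents do not support that. No test or alpha is affected.
- **Rescue is visible elsewhere.** Rescue, time to rescue and relapse are tabulated, with Kaplan-Meier curves (SAP sections 19 and 20), in all maintenance subjects.
- **Non-response is partly covered.** Missing-as-non-responder line plots are planned for IGA success and EASI-75 in the whole maintenance population. Entry required IGA 0/1 or EASI-75, so the EASI-75 plot is close to its subset. The IGA plot is less close, because it includes subjects who entered on EASI-75 alone. The whole-population tables 14.2.3.1.2.2 and 14.2.3.2.2.3 carry no method label and may show several methods, as SAP 10.3.3 plans for PP NRS in the Initial Period.
- **Redaction.** SAP 10.3.1 and 10.3.2 are blacked out, so the method is inferred from table titles and SAP 8.3.
- **Some loss will show.** SAP 17.2.5.2 bases percentages on subjects with an observation, so a falling count would be seen. It would not show how many of the missing had been rescued.

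A reader might also infer that the OC comparison could reverse. If exit and post-rescue response may differ freely by arm, the 25.5-point example spans −8.5 to +34.0. But −8.5 needs every rescued Q4W subject to stay without responding while every rescued placebo subject leaves, in a double-blind trial. With exit limited to 25–75% and post-rescue response to 25–60%, the span is −1.0 to +19.3. Nothing in the documents points to such opposite behaviour.

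**Conclusion.** The gap is real on the visible text, and modest. Among Week 16 responders, the two maintained-response tables are listed as OC only. Rescued subjects can count as successes, or leave the Week 48 denominator if they roll over between Week 32 and Day 322.

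The direction needs care. A reader might infer that the maintained-response percentages themselves could be biased either way. They cannot: against rescue as failure, each arm's OC percentage is equal or higher. Only the difference between arms can move in both directions, and it would often shrink if rescue is more frequent on placebo.

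The size cannot be fixed from the documents. The fall from 25.5 to 6.9 points and the rise from 24 to 30 are illustrations that rest wholly on assumed rates. Confidence is medium, because a rule in the redacted sections cannot be excluded. The existing plots and the rescue and relapse outputs limit the harm but do not replace a rescue-as-failure percentage in these two subsets, above all for IGA success.

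**What to change.** Add to the SAP table index, with a matching sentence in SAP 8.3, a version of 14.2.3.1.2.4 and 14.2.3.2.2.5 in which rescue, roll-over after rescue, and other missing data all count as not maintained. Show it beside the OC tables, with the number rescued and the number missing at Week 48 in each arm.

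Identify assessments missed because of COVID-19. Protocol Appendix 2 moves visits to remote contact when the site cannot be reached, and its remote list has no IGA or EASI; listing 16.2.1.7 already holds these cases. Counting them as failures has a cost of its own. At an equal 5% or 10% per arm, the 25.5-point difference becomes 0.95 × 25.5 = 24.2 or 0.90 × 25.5 = 23.0, and the Q4W rate falls from 76.5% to 72.7% or 68.9%.

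As a minor point of labelling, state the method on 14.2.3.3.2.4.

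The cost is one extra version of two tables. Missing-as-non-responder output is already planned for the maintenance line plots. Maintained-response percentages will generally be lower in every arm.
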